1.0 OBJECTIVES, ENDPOINTS AND ESTIMANDS

1.1 Objectives

1.1.1 Primary Objective

The primary objectives are:

Phase 1 Dose Escalation

- To determine the safety and tolerability of modakafusp alfa in combination with daratumumab SC.

Phase 2a Dose Finding

- To inform the RP2D of modakafusp alfa in combination with daratumumab SC.
- To provide a preliminary evaluation of the clinical efficacy of modakafusp alfa in combination with daratumumab SC as measured by ORR.

1.1.2 Secondary Objective(s)

Phase 1 Dose Escalation

- To characterize the PK profile of modakafusp alfa and daratumumab in the combination setting.
- To characterize antimyeloma activity as measured by ORR, DOR, PFS, and overall survival (OS).
- To characterize the immunogenicity of modakafusp alfa in combination with daratumumab SC.
- To characterize measurable (minimal) residual disease (MRD) negativity rate and duration of MRD negativity.

Phase 2a Dose Finding

- To determine DOR, clinical benefit rate (CBR), duration of clinical benefit (DCB), disease control rate (DCR), duration of disease control, time to progression (TTP), time to response (TTR), time to next treatment (TTNT), PFS, and OS.
- To further characterize safety and tolerability of modakafusp alfa in combination with daratumumab SC.
- To collect PK data for modakafusp alfa to support population PK and E-R analysis.
- To collect PK data for daratumumab SC to assess any potential impact of immunogenicity on daratumumab PK.

- To further characterize the immunogenicity of modakafusp alfa in combination with daratumumab SC.
- To characterize MRD negativity rate and duration of MRD negativity.

1.1.3 Additional Objective(s)

1.1.3.1 Exploratory Objectives

[REDACTED]

■ [REDACTED]
[REDACTED]

1.2 Endpoints

Patients' responses to the treatment will be determined per International Myeloma Working Group (IMWG) criteria in the current study.

1.2.1 Primary Endpoint(s)

The primary endpoints are:

Phase 1 Dose Escalation

- DLT incidences.
- Frequency and severity of TEAEs according to the National Cancer Institute Common Terminology Criteria for Adverse Events (NCI CTCAE), Version 5.0.

Phase 2a Dose Finding

- ORR, defined as the proportion of patients who achieved a confirmed response of PR or better during the study as assessed by the investigator.

1.2.2 Secondary Endpoint(s)

The secondary endpoints are:

Phase 1 Dose Escalation

- Summary statistics by dose level and cycle day for the following PK parameters for modakafusp alfa for Cycles 1 and 2:
 - Single-dose maximum observed serum concentration (C_{max}).
 - Time of first occurrence of C_{max} (t_{max}).

- Area under the serum concentration-time curve from time 0 to infinity (AUC_{∞}).
- Area under the serum concentration-time curve from time 0 to time of the last quantifiable concentration (AUC_{last}).
- Apparent serum modakafusp alfa terminal disposition rate constant.
- Apparent serum modakafusp alfa terminal disposition phase half-life.
- Clearance.
- Volume of distribution at steady state after intravenous (IV) administration.
- Summary statistics by dose level and cycle day for the following PK parameters for daratumumab for Cycles 1 and 2:
 - Single-dose C_{max} .
 - t_{max} .
 - Single-dose and multiple-dose observed concentration at the end of a dosing interval (C_{trough}).
 - AUC_{∞} .
 - AUC_{last} .
- ORR by the investigator.
- DOR by the investigator.
- PFS by the investigator.
- OS.
- ADA incidence and characteristics (eg, titer and specificity) and neutralizing antibody (NAb).
- Rate of MRD negative (MRD[-]) CR, at a threshold of 10^{-5} , with CR assessed by the investigator.
- Rate of MRD[-], at a threshold of 10^{-5} .
- Duration of MRD negativity, at a threshold of 10^{-5} .

Phase 2a Dose Finding

- DOR by investigator.
- CBR response of sCR, CR, very good partial response (VGPR), PR, or minimal responses (MR) by investigator.
- DCB by investigator.
- DCR (CBR + stable disease [SD]) by investigator.

- Duration of disease control by investigator.
- TTP by investigator.
- TTR by investigator.
- TTNT.
- PFS by investigator.
- OS.
- Frequency and severity of TEAEs according to the NCI CTCAE, Version 5.0.
- ADA incidence and characteristics (eg, titer and specificity) and NAb.
- Rate of MRD[-] CR, at threshold of 10^{-5} , with CR assessed by the investigator.
- Rate of MRD[-], at a threshold of 10^{-5} .
- Duration of MRD negativity, at a threshold of 10^{-5} .

1.2.3 Exploratory Endpoint(s)

1.3 Estimand(s)

Not applicable.

2.0 STUDY DESIGN

This is a global multicenter, open-label, phase 1/2a study designed to evaluate the safety, tolerability, pharmacokinetics (PK), pharmacodynamics (PD), and preliminary efficacy of modakafusp alfa in combination with daratumumab subcutaneous (SC) in patients with relapsed or refractory multiple myeloma (RRMM). The study will begin with a phase 1 dose escalation to evaluate the safety and tolerability of modakafusp alfa in combination with daratumumab SC. Two dose levels of modakafusp alfa in combination with daratumumab SC will be selected to be further explored in the randomized phase 2a dose finding part of the study. Patients will be randomized in a 1:1 ratio across 2 dose levels (DL1 or DL2) of modakafusp alfa in combination with daratumumab SC. The confirmed ORR assessed by the investigator per IMWG criteria will be determined as the primary efficacy endpoint of the phase 2a dose finding. The optimized recommended phase 2 dose (RP2D) of modakafusp in combination with daratumumab SC will be selected on the basis of integrated safety, efficacy, PK, and PD data from the current study and other relevant stud(ies).

Phase 1 Dose Escalation

The study will begin with a phase 1 dose escalation to evaluate the safety and tolerability of modakafusp alfa in combination with daratumumab SC during the Cycle 1 (28 days per cycle) dose-limiting toxicity (DLT) evaluation period and beyond. The proposed population in the phase 1 dose escalation will be patients with RRMM with at least 3 prior lines of therapy, including at least 1 proteasome inhibitor (PI), 1 immunomodulatory imide drug (IMiD), and 1 anti-CD38 monoclonal antibody (mAb) drug; or who are triple refractory to a PI, an IMiD, and an anti-CD38 mAb drug, regardless of the number of prior line(s) or therapy.

The dose escalation will follow the rolling six design with data collected in the dose escalation/de-escalation phase.

Phase 2a Dose Finding

Two dose levels of modakafusp alfa in combination with daratumumab SC doses will be selected from phase 1 dose escalation to be explored further in phase 2a open-label dose finding. Approximately 40 patients will be randomized 1:1 across 2 different dose levels (DL1 or DL2; N = ~20 at each dose level) of modakafusp alfa in combination with daratumumab SC. Eligible patients will include patients with RRMM who have received 1 to 3 prior lines of therapy, refractory to lenalidomide, and sensitive (nonrefractory) or naive to anti-CD38 mAb. The randomization will be stratified by the number of prior lines of therapy (1 vs 2 or 3). The primary endpoint is the confirmed ORR assessed by the investigator per IMWG criteria.

3.0 STATISTICAL HYPOTHESES AND DECISION RULES

3.1 Statistical Hypotheses

Not Applicable

CONFIDENTIAL

3.2 Statistical Decision Rules

Not Applicable

3.3 Multiplicity Adjustment

Not Applicable

4.0 SAMPLE-SIZE DETERMINATION

A total of approximately 58 patients will be enrolled in the study, including approximately 18 DLT-evaluable patients for the phase 1 dose escalation and approximately 40 patients (approximately 20 patients per arm) for the phase 2a dose finding.

The phase 1 dose escalation will accrue approximately 18 DLT-evaluable patients based on the algorithm of the rolling six design.

With approximately 20 patients per arm in the phase 2a dose finding, the probability of observing at least 1 AE given a different true AE rate is as follows:

True AE rate	5%	10%	15%	20%
Probability of observing at least 1 AE	64%	88%	96%	99%

With approximately 20 patients per arm in the phase 2a dose finding, the 95% exact binomial CIs associated with different observed ORR are as follows:

Observed ORR	60%	70%	80%
95% CI	(0.361, 0.809)	(0.457, 0.881)	(0.563, 0.943)
Width of the 95%CI	0.448	0.424	0.379

5.0 POPULATIONS

5.1 DLT-evaluable Population

The DLT-evaluable population includes all patients from the phase 1 dose escalation portion who experienced a DLT in Cycle 1 in the treatment phase of the study or have completed the Cycle 1 dose of modakafusp alfa and at least 75% of the planned dose of daratumumab SC. The DLT-evaluable population will be used to inform the 2 dose levels for modakafusp alfa to be selected in the phase 2a dose finding portion in combination with daratumumab SC.

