### 6.2.1 Phase 1 Dose Escalation

Approximately 18 patients will be enrolled in the phase 1 dose escalation/de-escalation. During phase 1, patients who are determined as DLT non-evaluable will be replaced. The definition of DLT-evaluable patients is provided in Section 13.1.1.

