### **8.1.2 Combination Agent Daratumumab SC**

#### **8.1.2.1 Dosage**

Daratumumab SC: 1800 mg QW for Cycles 1 and 2, Q2W for Cycles 3 to 6, and Q4W thereafter in 28-day cycles.

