### 8.3.2 Definition of DLT-Evaluable Patients

The DLT-evaluable population will include patients in the dose escalation/de-escalation phase who either experienced a DLT in Cycle 1 in the treatment phase of the study, or who have completed the Cycle 1 dose of modakafusp alfa and received at least 75% of the planned dose of daratumumab SC.

Patients who withdraw before completing the DLT assessment period for reasons other than a DLT, or who do not fulfill either of the criteria above, will not be evaluable for assessment of DLT for dose review decisions and will be replaced in the cohort.

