#### **8.6.1.5 Criteria for Discontinuation**

In the dose escalation, modakafusp alfa should be discontinued in patients experiencing an AE in Cycle 1 meeting criteria for a DLT for which the investigator considers that retreatment of the patient could be dangerous.

If the next cycle of modakafusp alfa is delayed for >14 days because of modakafusp alfa-related toxicities, study treatment should be discontinued unless the investigator considers that the patient will receive benefit continuing in the study. If treatment discontinuation is determined, the EOT visit should be completed within 30 days (+10 days) after the last administration of modakafusp alfa.

Patients who discontinue modakafusp alfa because of TEAEs assessed by the investigator as related *only* to modakafusp alfa may continue daratumumab SC treatment at the discretion of the investigator and with agreement by the sponsor.

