### **9.8 Discontinuation of Treatment With Study Drug and Patient Replacement**

Study drug must be permanently discontinued for patients meeting any of the following criteria:

- Patient experiences an AE or other medical condition that indicates to the investigator that continued participation is not in the best interest of the patient.

Treatment with study drug may also be discontinued for any of the following reasons:

- AE.
- Protocol deviation.
- Progressive disease.
- Symptomatic deterioration.
- Confirmed pregnancy.
- Study terminated by sponsor.
- Withdrawal by patient.
- Lost to follow-up.
- Other.

Once study drug has been discontinued, all study procedures outlined for the EOT visit will be completed as specified in the SOE ([Appendix A](#)). The primary reason for study drug discontinuation will be recorded on the eCRF.

In the case of study termination by the sponsor, eligible patients may have continued access to modakafusp alfa as described in Section [6.5](#).

Only patients who are withdrawn from treatment during Cycle 1 during the safety lead-in for reasons other than DLT will be replaced.

Note that some patients may discontinue study drug for reasons other than progressive disease before completing the full treatment course; these patients will remain in the study for posttreatment assessments as outlined in the SOE ([Appendix A](#)) until progressive disease occurs.

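### The DLT-evaluable set in protocol 13.1.1 and SAP 5.1 omits the early-withdrawal exclusion in protocol 8.3.2, so the reported DLT denominator can include partly observed patients

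*SAP*

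**What the plan says.** Three sections define the same named population.

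- **SAP 5.1 and protocol 13.1.1** have two routes in. A patient qualifies with a DLT in Cycle 1. Otherwise the patient must "have completed the Cycle 1 dose of modakafusp alfa and at least 75% of the planned dose of daratumumab SC". Neither section says anything about early withdrawal or about completing the observation period.
- **Protocol 8.3.2, paragraph 1** gives the same two routes, beginning with patients "who either experienced a DLT in Cycle 1 in the treatment phase of the study".
- **Protocol 8.3.2, paragraph 2** adds an exclusion. "Patients who withdraw before completing the DLT assessment period for reasons other than a DLT", or who meet neither route, "will not be evaluable for assessment of DLT for dose review decisions and will be replaced in the cohort". The withdrawal limb is separate from the dosing limb, so a patient can pass the dosing test and still be excluded.

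Protocol 6.2.1 says that non-evaluable patients are replaced, but it sends the reader to the version without the exclusion: "The definition of DLT-evaluable patients is provided in Section 13.1.1". Protocol 9.8 has its own replacement sentence: "Only patients who are withdrawn from treatment during Cycle 1 during the safety lead-in for reasons other than DLT will be replaced".

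On reporting, DLT incidence is one of the two Phase 1 primary endpoints, and protocol 13.1.8 tabulates it on the DLT-evaluable population. SAP 6.7 puts all safety analyses on the safety population. SAP 6.7.1 plans a by-patient listing of DLTs and no table of DLT counts over evaluable patients.

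**The concern.** A DLT rate is interpretable only if patients counted as free of DLT were watched for the period in which one could occur. Protocol 8.3.2 protects that condition for dose review. The analysis-set definitions do not, because three weekly daratumumab injections can satisfy the dosing test well before Cycle 1 ends.

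Following SAP 5.1 exactly therefore adds a partly observed patient to the denominator as DLT-free. Dose review treats the same patient as non-evaluable and has that patient replaced. The clinical study report and the dose-review record could then show different denominators for one dose level. SAP 6.2 reports the size of each population, so the difference would be visible, but nothing would explain it.

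**Working it through.** **Plan's own figure.** The only planned count is approximately 18 DLT-evaluable patients (protocol 13.2, SAP 4.0). The documents give no formula. It agrees with 3 dose levels (80, 120 and 240 mg) × 6 = 18. No planned DLT rate is given to reproduce.

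**When the dosing test is met.** Daratumumab is given at "1800 mg QW for Cycles 1 and 2", and the schedule of events places the Cycle 1 injections on Days 1, 8, 15 and 22. I assume that the planned dose means these four injections, which the text does not state.

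- Planned: 4 × 1800 = 7200 mg
- 75% of planned: 0.75 × 7200 = 5400 mg = 3 injections, reached on Day 15
- Days left in the 28-day cycle: 28 − 15 = 13, or 13/28 = 46%
- With the ±2-day visit window (Day 13 to Day 17): 15 to 11 days left

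The mismatch does not depend wholly on that assumption. If all four injections were needed, a patient leaving just after Day 22 would still pass with 28 − 22 = 6 days unobserved.

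**Classification of a DLT-free patient who leaves after the Day 15 injection for another reason.**

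- Protocol 13.1.1 and SAP 5.1: modakafusp alfa dose completed, 75% reached, so evaluable and DLT-free.
- Protocol 8.3.2, paragraph 2: left before the period ended, not for a DLT, so not evaluable and replaced.

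**Effect at one dose level.** Take six patients evaluable under 8.3.2, including a DLT-free replacement, plus the one who left. Intervals are 95% Clopper-Pearson.

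- One DLT, 8.3.2 set: 1/6 = 16.7% (0.4% to 64.1%)
- One DLT, SAP 5.1 set: 1/7 = 14.3% (0.4% to 57.9%)
- Difference: 16.7 − 14.3 = 2.4 percentage points lower
- No DLT, 8.3.2 set: 0/6, upper limit 1 − 0.025^(1/6) = 45.9%
- No DLT, SAP 5.1 set: 0/7, upper limit 1 − 0.025^(1/7) = 41.0%

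**How likely is one such withdrawal?** The documents give no rate. If a proportion w of patients left in this way, the chance of at least one among 18 would be 1 − (1 − w)^18. For assumed values of w:

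- w = 2%: 30.5%
- w = 5%: 60.3%
- w = 10%: 85.0%

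**The case against.** The strongest defence is that the two rules serve different purposes. Paragraph 2 of 8.3.2 limits itself to dose-review decisions, while 13.1.1 and SAP 5.1 define an analysis set. The documents do not draw that line. All three use the same name, 6.2.1 ties replacement to the 13.1.1 definition, and no passage says which rule prevails. Even if the separation were intended, the reported rate would still rest on patients who were not observed throughout.

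It is also fair to say that the SAP does not cancel the protocol's table. Protocol 13.1 says that departures from its analyses will be indicated in the SAP, and none is indicated here. The missing table is therefore a gap in completeness, not a change of analysis. The objection that the endpoint is descriptive also stands: SAP 3.1 to 3.3 set no hypotheses, decision rules or multiplicity adjustment.

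A reader might infer more than the documents support:

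- **That an observed DLT could be dropped.** Section 8.6.1.5 calls for discontinuation only after a Cycle 1 event "meeting criteria for a DLT for which the investigator considers that retreatment of the patient could be dangerous". A patient could therefore have a DLT, stay on treatment and later leave for another reason, and paragraph 2 of 8.3.2 read alone would exclude that patient. Read with paragraph 1, which includes anyone with a Cycle 1 DLT, it does not. Section 8.4 also acts on observed DLTs whatever the number enrolled, and the SAP listing covers all escalation patients.
- **That the gap is larger before replacement,** for example 1/6 against 1/5. Section 8.3.2 requires replacement, so that contrast is temporary.
- **That escalation is affected,** because 13.1.1 and SAP 5.1 say the set informs the Phase 2a doses. Section 8.3.2 expressly governs dose review.
- **That the Cycle 2 delay criterion falls outside the DLT period.** Under SAP 6.1.1.2 a new cycle starts only when modakafusp alfa is given, so a patient whose Cycle 2 is delayed is still in Cycle 1. This is in any case a separate matter from who is evaluable.

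**Conclusion.** The mismatch is real and minor. SAP 5.1 and protocol 13.1.1 admit DLT-free patients whom 8.3.2 makes non-evaluable. Each one adds 1 to the denominator and nothing to the DLT count, so the tabulated rate falls, or stays at zero with a tighter upper limit if there was no DLT. In the worked case the fall is 2.4 percentage points, or 4.9 points on the upper limit when no DLT occurs (45.9 − 41.0).

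The Day 15 timing rests on reading the planned dose as the four Cycle 1 injections. The effect arises only if at least one patient leaves in this way; with none, the definitions give the same set. What is at stake is the reporting of a descriptive primary endpoint. The absence of the DLT table from the SAP holds whether or not anyone withdraws.

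**What to change.** 1. Reconcile protocol 8.3.2, 6.2.1 and 13.1.1 and SAP 5.1 into one analysis-set definition, and have the other sections refer to it. A DLT-free patient who did not complete the DLT period should not be in the DLT-incidence denominator, even if the dosing test is met. A patient with an observed Cycle 1 DLT should stay in, whatever the reason for leaving later. Paragraph 2 of 8.3.2 should not be copied unchanged, because it does not state that second point.
2. In the same text, say whether the planned daratumumab dose means the four Cycle 1 injections, and whether withdrawal means from treatment or from the study.
3. Add to SAP 6.7.1 a table of DLT n/N by dose level on this set, as protocol 13.1.8 specifies, and mark it as an exception to the safety-population rule in SAP 6.7.
4. As an editorial point, reconcile the replacement sentence in 9.8 with 8.3.2. Its reference to a safety lead-in appears to be leftover text: Appendix G records that the same phrase was replaced in 8.6.1.5.

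The cost is wording in the two documents and one table, with no new data. If a protocol amendment is not wanted, the SAP can carry the reporting part as an indicated departure, which protocol 13.1 allows.

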5.2 Response-evaluable Population

The response-evaluable population includes all patients who receive at least 1 dose, even an incomplete dose, of any study drug, have a disease assessment at screening (baseline evaluation), and at least 1 postbaseline disease assessment. The response-evaluable population will be used

for the primary analysis for ORR in phase 1 dose escalation portion and sensitivity analysis in phase 2a dose finding portion.

5.3 Safety Population

The safety population will include all patients who receive at least 1 dose, even an incomplete dose, of any study drug. Patients in this set will be analyzed according to the actual treatment they received. The safety population will be used for the baseline assessment and efficacy analysis except for the endpoints of PFS, OS and TTP in Phase 2a. It will be also used for the safety analysis.

5.4 Per-Protocol Population

The per-protocol population is a subset of subjects in the safety population who do not have major protocol deviations that are considered to impact efficacy outcomes. The list of major protocol deviations is documented and maintained by the sponsor on an ongoing basis and will be finalized prior to database lock. The per-protocol population will be used in the sensitivity efficacy analysis for endpoint of ORR if patients excluded due to major protocol deviation are deemed to have significant impact on the analysis of primary endpoints.

5.5 Intent-to-treat (ITT) Population

The ITT population will include all patients who are randomized. Patients in this set will be analyzed according to the treatment they are randomized to receive, regardless of any dosing errors. The ITT population will be used for the main efficacy analysis for endpoints of PFS, OS and TTP.

5.6 Pharmacokinetic Population

The pharmacokinetic (PK) population includes patients from the safety population with sufficient PK data to reliably report 1 or more PK parameters.

5.7 Immunogenicity-evaluable Population

The immunogenicity-evaluable population includes patients who received at least 1 dose of modakafusp alfa + daratumumab SC (partial or complete) with a baseline assessment and at least 1 postbaseline immunogenicity assessment. Immunogenicity analysis will be primarily based on the immunogenicity-evaluable population.

6.0 STATISTICAL ANALYSIS

6.1 General Considerations

All statistical analyses will be conducted using SAS® Version 9.4 or later.

For categorical variables, the count and proportions of each possible category value will be tabulated. The denominator for the proportion will be based on the number of subjects in the

CONFIDENTIAL

populations. For continuous variables, the mean, median, standard deviation, minimum, and maximum values will be presented for all patients in the relevant population.

All 95% confidence intervals will be reported as 2-sided. No formal statistical comparisons will be performed between dose levels.

Baseline values are defined as the last observed value before the first dose of any study drug.

